12.0 Provisions to Monitor the Data to Ensure the Safety of Subjects*

We will follow the NIAAA guidelines for administration of alcohol, including attention to informed consent; selecting participants that have no known increased risk of alcohol dependence; great attention to confidentiality; restriction to participants who regularly consume alcohol rather than alcohol-naïve individuals; exclusion of pregnant women; low alcohol exposure for the intervention period of 3 weeks; access to medical backup services; and compensation for participation.

[name], a practicing primary care internist, [name], an oncology internist, or an oncology internist identified by [name] will oversee data safety. They will monitor laboratory results from the scheduled visits on a real-time basis for all participants. They will ensure comprehensive monitoring and entry of all safety-related data in the REDCap electronic research management system, distinguishing between serious adverse events, non-serious adverse events, and unanticipated problems following the BIDMC's IRB guidelines. The study team will meet every month to discuss the ongoing health and safety of participants.

At all clinic visits, we will measure vital signs and body measurements. A member of the research team will call participants once per week to ask about any reasons to speak to or meet with a health practitioner and any other health changes. At all visits and on all weekly calls, we will encourage participants to contact us about any health concerns or questions.

We will also obtain lab assays for a hepatic panel, lipid panel, and complete blood count. We will discontinue enrollment and immediately refer for treatment any participant who

- Develops liver function test abnormalities greater than 2X the upper limit of normal or
- Experiences 15% change in their white blood count, hemoglobin level, or platelet count that results in values outside the normal range or
- Experiences a doubling of their triglyceride levels that results in values outside the normal range

following the three weeks of consuming white wine.

Participants who report any excess use of their assigned beverage per week will receive additional intensive surveillance by telephone, and we will discontinue enrollment if excessive alcohol use persists.

If participants report more than the assigned amount of wine during any study visit including the final visit, on a questionnaire, or during a phone call with study staff, [name] will speak with them to determine if any evidence of alcohol use disorder or at-risk drinking is present. If there is evidence of problem drinking, they will be immediately referred for treatment. Addiction specialists, including

psychopharmacologists and clinical social workers, practice within the Healthcare Associates multidisciplinary clinic and are available on-call at all times.

We will report adverse events as follows:

1. **Unexpected fatal or life-threatening adverse events** will be reported to the BIDMC institutional review board (the Committee on Clinical Investigations - CCI) and the BIDMC General Clinical Research Center (GCRC) Research Subject Safety Office (RSSO) by telephone or in person within **one business day** of notification, and followed by a formal written report within **seven calendar days**.
2. All other **expected and unexpected serious adverse events** will be reported to the CCI and the GCRC RSSO within **seven calendar days**.
3. We will also provide the GCRC RSSO with an **annual summary of adverse events** (including anticipated, non-serious adverse events), delineated by category and number in addition to that provided to the CCI.

Any serious adverse event will lead to a cessation of enrollment until the relationship between the adverse event and the study conduct is determined.

The study team will meet at least once per month to discuss the information collected from the CRC visits, lab results, weekly calls and REDCap surveys, and any calls from participants about other concerns or health changes. We will discuss the safety of trial enrollment and any concerns and whether we should propose any changes to the protocol.

In addition to this intense safety oversight, we will develop an independent Data and Safety Monitoring Board (DSMB) comprised of a general internist or oncologist with expertise in clinical trial conduct, an alcohol expert (who may also be a physician), and a biostatistician. The DSMB will meet every 6 months during the trial and more frequently as needed. We will notify the DSMB immediately if any unexpected life-threatening or fatal adverse events occur. They will provide reports after each meeting outlining the safety of the trial and delineate any plans for interruption or discontinuation of the trial.

The content of the Data and Safety Monitoring Reports will include details such as

- a. Number of participants screened, reasons potential participants excluded, the number enrolled
- b. Frequency, mean, min/max of all laboratory safety assays, e.g., elevations in liver function tests, severe neuropsychiatric disturbances, or changes in vital signs
- c. Quality and completeness of the study data: frequency of missing or erroneous data, and frequency of outliers
- d. Safety data by treatment period, including frequency of adverse events, serious adverse events, and any data that allows for comparisons of safety among alcohol and non-alcohol dietary periods, e.g., clinical laboratory data, treatment retention, and reasons for participant dropout.

- e. Individual participant data will be available for DSMB review as needed. In the assessment of serious adverse events, the DSMB will review each case, including treatment group assignment.

The DSMB will stop the trial if there is evidence of any of the following conditions:

- a. Clear evidence of harm
- b. No likelihood of demonstrating treatment benefit (futility)
- c. Overwhelming evidence of the benefit of treatment

We have no reason to anticipate that alcohol is beneficial for sex hormone levels. Rather, we are testing whether the constant use of aromatase inhibitor therapy throughout study enrollment lowers the impact of alcohol consumption on within-person changes in sex hormone levels. If the results of the lab results indicate that the low alcohol intake is harmful as defined by the DSMB, the DSMB will stop the trial.

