3.0 Inclusion and Exclusion Criteria*

We aim to identify postmenopausal women with estrogen receptor-positive (ER+) breast cancer who typically consume at least one alcoholic drink per week but not more than two servings per day and are currently prescribed aromatase inhibitors including anastrozole (Arimidex®), letrozole (Femara®), and exemestane (Aromasin®). These drugs are only prescribed to postmenopausal women who have been diagnosed with estrogen receptor positive (ER+) breast cancer, the subtype where alcohol has been found to increase breast cancer incidence.

Inclusion Criteria:

- ER+ breast cancer
- Female sex at birth
- Postmenopausal, either natural or induced
- Self-reported consumption of at least one alcoholic drink per week but not more than two servings per day
- Currently prescribed aromatase inhibitors including anastrozole (Arimidex®), letrozole (Femara®), and exemestane (Aromasin®)
- Documented liver function test results below 1.5X the upper limit of normal within 12 months of screening

Exclusion criteria:

- Self-reported consumption of more than two drinks per day, a previous or current history of alcohol abuse based on standard questionnaires (AUDIT \geq 8), or consumption of 4 or more drinks in one day within the last 6 months
- Currently undergoing cytotoxic chemotherapy or radiation planned in the next two months
- Any surgery planned in the next two months
- Alcohol flushing syndrome
- Current use of any pharmaceutical agent contraindicated with alcohol, including warfarin, dual antiplatelet therapy, and metronidazole
- Hemoglobin A1c $>$ 8% or a fasting glucose result above 180 mg/dL within 6 months of screening

- Unable to speak or understand English
- Unable to understand and provide informed consent, as judged by the study team
- Uncertain ability to complete the protocol, as judged by the study team

We will not include adults unable to consent, individuals who are not yet adults, pregnant women, or prisoners.

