9.0 Procedures Involved*

This is an unblinded randomized controlled crossover trial to examine whether 3 weeks of light alcohol consumption causes a short-term change in sex hormone levels compared to levels following 3 weeks of white grape juice consumption among postmenopausal women with estrogen receptor-positive (ER+) breast cancer taking an aromatase inhibitor. In this design, participants are compared to themselves at different times, with the sequence of the two treatment arms assigned by randomization. In other words, half of the women will be randomized to consume one serving of white wine every day for three weeks followed by one serving of white grape juice every day for three weeks, and half of the women will be randomized to three weeks of white grape juice followed by three weeks of white wine. To prevent a potential carryover effect of the drink in the first period affecting hormone levels in the second treatment period, we will ask participants to refrain from drinking any alcohol or grape juice for two weeks before starting each treatment arm. The women will know when they are supposed to drink the wine and when they are supposed to drink the grape juice.

Recruitment:

We will present the trial protocol and eligibility criteria at a meeting for the six medical oncologists and three nurse practitioners who provide outpatient care at the BIDMC BreastCare Center and ask for their assistance to recruit patients from their practice who may be eligible and interested in participating in our trial.

We will review medical records for patients receiving care in the BreastCare Center or Healthcare Associates (HCA), BIDMC's primary care practice, to see if they meet the eligibility criteria, and contact their health provider about their fitness to participate. Unless their provider recommends otherwise, we will mail an invitation letter to patients who appear to be eligible and ask them to contact us if interested. If they do so and remain interested, we will arrange a screening visit. We will also call participants who have received letters and have upcoming clinical appointments to remind them of the study and to determine if they would like to arrange a screening visit in conjunction with that appointment. We will also continue to place flyers and brochures in the BreastCare Center so that women who are interested in the study can reach out to us.

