We are submitting a request for a waiver of HIPAA authorization to obtain protected health information for potentially eligible women receiving care at the BIDMC BreastCare Center to confirm eligibility. Institutions will register eligible

participants in the Clinical Trials Management System (CTMS) OnCore as required by DF/HCC Policy REGIST-101.

Screening Visit:

If a referred patient is interested in learning more about the study, we will invite her to meet with a member of the research team in a private room at the BIDMC BreastCare Center. The study team member will explain the study, obtain informed consent, and confirm eligibility. An MD is not required for the consent process. No study procedures will be performed prior to obtaining informed consent. If the patient has not had liver function measured in the past 12 months, we will conduct a liver function test at their screening visit. If a hemoglobin A1c or fasting glucose test is not available, we will refer them to their physicians until we can document clinical control. We will obtain information on medical history, including an assessment of their usual frequency of alcohol consumption (using the Alcohol use Disorders Identification Test (AUDIT), the type of aromatase inhibitor therapy prescribed, and demographic and medical characteristics,

Aromatase inhibitors are only prescribed to women who are postmenopausal, either naturally or artificially induced. If any women report that they are pre-menopausal, sexually active, and not using an effective form of contraception, we will counsel them that these medications are teratogenic and they will be referred back to their providers. Participants found ineligible will be thanked for their time but they will not be invited for the baseline visit (Study Visit 1). Either the primary investigator ([name]) or another physician involved in the study will review the screening results to confirm eligibility. Eligible participants will begin a two-week run-in period in which they will refrain from alcohol and grape juice (washout period 1).

Study Visit 1 (Baseline):

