If the participant confirms that she did not drink alcohol or grape juice for the past two weeks, she will return for visit 2 after fasting for 12 hours. The BIDMC CRC nurses will draw 100 mL (approximately 7 tablespoons) of blood for real-time processing of a basic metabolic panel and safety monitoring (complete blood count and hepatic panel). We will store the remaining sample for analyzing sex hormone levels as soon as all participants complete the study. The CRC nurses will conduct the blood draw, specimen processing, and transportation to Quest Diagnostics in accordance with their pre-specified procedures.

The CRC research nurses will conduct safety monitoring at each study visit. Using their standard protocols, they will perform repeated measurements of vital signs, including height (at baseline), weight, systolic and diastolic blood pressure, and heart rate. They will measure supine blood pressure as the average of the final 2 of 3 measurements following at least five minutes of rest using an automated cuff device calibrated at least monthly. They will measure weight with the participant wearing light clothing and standing on a digital scale with handrails.

Using the REDCap randomization module, we will randomly allocate women to a sequence of either white grape juice followed by white wine or to a sequence of white wine followed by white grape juice. One drinking period consists of 3 weeks of one serving (5 oz≈14 g alcohol) of white wine consumption daily and the other drinking period consists of 3 weeks of a calorically equivalent serving (6 ounces) of (alcohol-free) white grape juice. At the beginning of the white wine drinking period, the participants will receive one 3L box and one 500 mL box of Bota Box Chardonnay, a commercially available white wine that is 13% alcohol by volume for the three weeks of one serving (5 ounces) of white wine consumption daily. At the beginning of the white grape juice drinking period, the participants will receive one 96-ounce bottle and one 64-ounce bottle of Welch's 100% White Grape Juice for the three weeks of a calorically equivalent serving (6 ounces) of (alcohol-free) white grape juice each day. There will be no blinding of the alcoholic beverages; all participants will know when they have been randomized to drink the white wine and when they have been randomized to drink the grape juice.

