After obtaining IRB approval, we will work with the CRC to finalize the plans to purchase, store and transfer the white wine and white grape juice to participants. We will distribute the three-week supply of wine or grape juice and a standardized labeled measuring cup to ensure that participants consume the correct amount each day. We will give the participants an information sheet, advising them to refrain from all alcohol and grape juice except their assigned drink and to maintain their typical patterns of diet and activity throughout the study. For the three weeks of white wine intake, we will advise participants to drink their daily serving at a time when they will not drive or operate machinery in subsequent hours. We will also provide a paper calendar for participants to record their daily alcohol and grape juice intake and tell them that we will review this calendar with them on our weekly phone calls.

Study Visit 2:

At the end of the 3-week drinking period, the participant will come to the BIDMC CRC, and a nurse will draw 90 mL (approximately 6 tablespoons) of blood for safety measures and sex hormone levels. They will also take vital signs and measure weight. We will ask participants to bring leftover drinks to this visit so that we can measure the remaining amount as an indicator of adherence. We will ask participants to refrain from drinking any alcohol or grape juice for the next two weeks (washout period 2).

Study Visit 3:

At the end of the 2-week washout period, the participant will come to the BIDMC CRC, and a nurse will draw 90 mL (approximately 6 tablespoons) of blood for safety measures and sex hormone levels. They will also take vital signs and measure weight. We will then distribute the second beverage to consume daily for the following 3 weeks.

Study Visit 4:

At the end of the 3-week drinking period, the participant will come to the BIDMC CRC, and a nurse will draw 90 mL (approximately 6 tablespoons) of blood for safety measures and sex hormone levels. They will also take vital signs and measure weight. We will ask participants to bring leftover drinks to this visit so that we can measure the remaining amount as an indicator of adherence.

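### The only mandatory liver stopping rule after entry takes effect once the wine weeks are over, so it can prevent no wine serving; panels drawn before wine carry no mandatory stop

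*Combined protocol and SAP*

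**What the plan says.** **Entry.** Section 3.0 requires "Documented liver function test results below 1.5X the upper limit of normal within 12 months of screening". Under Section 9.0 a liver test is done at screening only if none was done in the past 12 months. The health provider is consulted before an invitation is mailed (the team will "contact their health provider about their fitness to participate"), and the principal investigator or "another physician involved in the study will review the screening results to confirm eligibility".

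**After entry.** Hepatic panels are drawn at Visits 1, 2, 3 and 4 (Sections 8.0 and 9.0). Section 12.0 sets the only numeric liver limit after entry, a mandatory discontinuation and referral. Its trigger is "Develops liver function test abnormalities greater than 2X the upper limit of normal or"; blood count and triglyceride triggers follow. A separate line after all three reads "following the three weeks of consuming white wine".

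**Dispensing.** At Visit 1 the panel is drawn, the woman is randomised and the first beverage is handed over. At Visit 3 the panel is drawn, and the text continues: "We will then distribute the second beverage to consume daily for the following 3 weeks".

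**Review without a fixed limit.** Section 12.0 says of the overseeing physicians: "They will monitor laboratory results from the scheduled visits on a real-time basis for all participants". Section 9.0 (Safety and Adherence) obliges the safety monitor to follow up women with concerning results. Section 13.0 permits, but does not require, ending participation for unacceptable alcohol risk (ground a) or when entry criteria no longer hold (ground d).

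**The concern.** The plan itself judges that a liver result above twice the upper limit of normal (ULN) calls for compulsory action. It then confines that action to the time when the woman has finished the wine. Section 14.0 names worsening of existing liver disease as a risk of the alcohol. The panels on which stopping could avert that exposure are the ones drawn before wine, and those have no mandatory limit.

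Wine-first women are the most exposed. For one who qualifies on an older record, Visit 1 gives the first current liver result, yet she leaves that visit with the wine. At stake is avoidable exposure of an occasional woman with a newly abnormal liver test. The hormone comparison is not at stake.

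**Working it through.** **Inputs** (schedule table in Section 9.0): panels on days 15, 36, 50 and 72 (Visits 1 to 4); drinking periods on days 15–35 and 51–71; one serving a day.

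**Scheduled wine servings.** Wine-first: 35 − 15 + 1 = 21. Juice-first: 71 − 51 + 1 = 21.

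**What the rule can prevent as written.**

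| Sequence | First panel covered | Servings already scheduled | Servings left | Study days left |
|---|---|---|---|---|
| Wine-first | Visit 2, day 36 | 21 | 21 − 21 = 0 | 72 − 36 = 36 |
| Juice-first | Visit 4, day 72 | 21 | 21 − 21 = 0 | 72 − 72 = 0 |

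The ±4-day visit window changes the servings taken to about 17–25 (21 − 4 to 21 + 4). The zero stays, because the post-wine visit ends the wine period.

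**Panels before wine with no mandatory limit.** Wine-first: one (Visit 1). Juice-first: three (Visits 1, 2 and 3).

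**What the same limit could prevent if it covered every panel.** Let L be the days from draw to result. The documents do not state L. Sections 8.0 and 9.0 say the safety assays are measured within 72 hours; Section 11.0 says the samples are sent to the laboratory within 72 hours. L = 0 and L = 3 are therefore assumptions, and L could exceed 3 if 72 hours is the dispatch time.

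| Panel | L = 0 | L = 3 |
|---|---|---|
| Wine-first, Visit 1 (day 15) | 21 of 21 | days 18–35: 18 of 21 |
| Juice-first, Visit 1 (day 15) | 21 of 21 | 21 of 21 |
| Juice-first, Visit 2 (day 36) | 21 of 21 | 21 of 21 |
| Juice-first, Visit 3 (day 50) | 21 of 21 | days 53–71: 19 of 21 |

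In general, a wine-first woman takes L servings before her Visit 1 result: 0 if it is same-day, 3 if it takes 72 hours, more if it is slower.

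**Age of the entry result at first wine, wine-first.** Taking 12 months as 365 days and screening as day 0: up to 365 + 15 = 380 days, before visit windows. In juice-first women its age hardly matters, since the Visit 1 and Visit 2 panels are drawn 50 − 15 = 35 and 50 − 36 = 14 days before wine is dispensed.

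**Dose in context.** Seven servings a week, against a permitted usual intake of 1 to 14 a week (one a week to two a day), is 7/14 = 0.5 to 7/1 = 7 times usual intake.

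**The case against.** The strongest reply is that the team is not blind to these panels. Physicians watch results as they arrive, the safety monitor must follow up concerning ones, and Section 13.0 allows stopping on two relevant grounds. Ground (d) brings in the 1.5X ULN entry limit, which is stricter than 2X. In a single-site trial of 20 women, judgement may serve well. Most of this stands: a reader might infer that pre-wine panels go unreviewed, and the documents contradict that. What is missing is only a required threshold and a required stop.

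Zero of 21 is also partly built in. No blood is drawn during a drinking period, so any post-exposure rule prevents nothing, and a rule worded around developing an abnormality is meant to detect toxicity. That is fair. The rule still triggers referral in both sequences and, in wine-first women, stops the remaining washout and juice. The figure describes the rule's reach, not harm.

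The closing phrase could be read as qualifying the triglyceride trigger alone, in which case the liver limit already covers every panel. Its placement on its own line after all three triggers favours the wider reading. If the narrower one was intended, the text needs a clarifying sentence, and the timing gap at Visit 1 remains.

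Two stronger readings are not supported. One is that wine-first women take three servings before the result, as if that were a bound: no result time is stated, so the number could be lower or higher. The other is that juice-first women start wine on a year-old liver test: two on-study panels come well before their wine is dispensed.

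**Conclusion.** The point holds, at minor severity. As laid out, the one mandatory liver limit after entry can prevent 0 of 21 wine servings in either sequence, and the panels drawn before wine carry no mandatory stop. The consequence falls mainly on wine-first women (about 10 of 20) who enter on an older result, because nothing ties the first serving to a reading of the Visit 1 panel. In juice-first women the gap is smaller, since there is time to act on two earlier panels.

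This rests on reading the closing phrase as governing all three triggers, and on the nominal schedule. The number of servings before a Visit 1 result depends on an unstated turnaround. The documents give no rate of results above 1.5X or 2X ULN, so no probability of harm is claimed. All participants already drink, so the safety gain is modest, and the primary endpoint is not affected.

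**What to change.** 1. In Section 12.0, apply the existing >2X ULN discontinuation and referral rule to every on-study hepatic panel (Visits 1 to 4). Leave the blood count and triglyceride rules as they are.
2. In Section 9.0, require a study physician to check the Visit 1 and Visit 2 panels before wine is dispensed at Visit 3 to juice-first women. Require the physician to act on the Visit 1 panel (wine-first) and the Visit 3 panel (juice-first) as soon as each result is available.

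These take a few sentences and need no new visit, tube or assay. Some servings may still precede the Visit 1 result in wine-first women, or the Visit 3 result in juice-first women.

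Optional: hold the first beverage in both sequences until the Visit 1 result is confirmed. This closes the Visit 1 gap but has costs:
- If 72 hours is the result time, the hold lasts about 0–3 days, washout 1 becomes up to 14 + 3 = 17 days, and Visit 4 moves to at most about day 72 + 3 = 75. If 72 hours is only dispatch, the hold is longer and could exceed the four-day extension that Section 9.0 accepts for delayed visits.
- It lengthens washout 1 but not washout 2, and the mixed model in Section 11.0 has no period term.
- Because randomisation is at Visit 1, it may leave an occasional randomised woman who never starts. Section 23.0 enrols until 20 complete, so she can be replaced, but the intention-to-treat analysis has to account for her.

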8.0 Study Endpoints*

We will examine within-person changes in blood levels of estradiol, testosterone, dehydroepiandrosterone sulfate (DHEAS), and sex hormone-binding globulin (SHBG) after three weeks of one serving of white wine daily compared to levels after three weeks of one serving of white grape juice daily.

At visits 1, 2, 3, and 4, the BIDMC Clinical Research Center (CRC) nurses will obtain a fasting blood sample. Within 72 hours, Quest Diagnostics will measure hepatic function, a complete blood count, and following visits 2 and 4, they will conduct a lipid panel. On our weekly phone check-ins, we will ask about recent health events such as unscheduled hospitalizations or any symptoms that have developed since the last meeting.

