Blood Samples: The nurse will obtain blood samples in the morning after the last day of each 2-week washout period and each 3-week dietary period. We will schedule blood draws for time windows of up to ± 4 days of the end of the prior washout or drinking period. If the visit is delayed for up to four days, we will ask participants to continue the protocol (washout, white wine, or white grape juice) for the additional days. At visit 1, the nurse will draw 100 mL (approximately 7 tablespoons) of blood and at visits 2, 3, and 4, the nurse will draw 90 mL (approximately 6 tablespoons) of blood. They will draw one 10 mL tube for each of the 10 assays: complete blood count, hepatic function panel, basic metabolic panel (only at visit 1), DHEAS, FSH, LH, SHBG, estradiol, testosterone, and progesterone. This amount is in accordance with the BIDMC Committee on Clinical Investigations (CCI) Blood Volume Safety Guidelines.

The CRC staff will centrifuge the blood samples for the complete blood count, hepatic function panel, basic metabolic panel, and sex hormones for 15 min at 2000x g and 4°C between 15 and 30 min after collection. They will aliquot the plasma and serum in labeled 250 μ l cryovials and store the samples at -80°C in CRC freezers. The CRC will send blood samples to Quest Diagnostics. The safety measurements will be conducted within 72 hours of collection. At the end of the study, they will send frozen samples from each visit to Quest Diagnostics for analysis of sex hormones. The CRC nurses will conduct the blood draws, specimen processing, and transfer to Quest Diagnostics in accordance with the CRC's established protocols to maintain the quality of the specimens and to protect the privacy of the participants.

Safety and Adherence: A member of the research team will call participants once per week to ask about any changes in health, to remind the participant to complete the weekly online questionnaire about lifestyle factors, and to address any questions that they may have about their participation in the study. A safety monitor will oversee patient safety by regularly monitoring participants' vital sign and body measurements from clinic visits, lab results for liver function, complete blood count, and triglycerides and responses to questions from the weekly check-in calls about any changes in health, and they will follow up with any participant whose results are concerning.

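### The triglyceride-doubling safety rule has no reference value for wine-first women at Visit 2, because lipid panels follow only the two drinking periods

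*Combined protocol and SAP*

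**What the plan says.** Section 12.0 sets three laboratory triggers. The consequence is introduced by "We will discontinue enrollment and immediately refer for treatment any participant who", and the list is closed by the condition "following the three weeks of consuming white wine". The triggers are:

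- liver function tests above 2 times the upper limit of normal;
- "Experiences 15% change in their white blood count, hemoglobin level, or platelet count that results in values outside the normal range";
- "Experiences a doubling of their triglyceride levels that results in values outside the normal range".

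On timing, Section 8.0 says of the laboratory that "following visits 2 and 4, they will conduct a lipid panel". The assessment table in Section 9.0 counts 2 lipid panels per woman, against 4 hepatic panels and 4 blood counts. The Visit 1 draw is described as "real-time processing of a basic metabolic panel and safety monitoring (complete blood count and hepatic panel", with the remainder stored for hormone assays once all women have finished. The Blood Samples paragraph allots one tube to each of "complete blood count, hepatic function panel, basic metabolic panel (only at visit 1), DHEAS, FSH, LH, SHBG, estradiol, testosterone, and progesterone". Under Safety and Adherence, the safety monitor's regular review covers "lab results for liver function, complete blood count, and triglycerides".

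**The concern.** The triglyceride trigger is a ratio joined to a range check. A post-wine result can show that a value is out of range, but it cannot show a doubling without a value from before the wine. In the wine-first sequence the plan schedules no such value.

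What is at stake is the prespecified numeric trigger for referral. Without a reference, staff following the protocol alone would have to find a comparator case by case, and the two sequences would be judged differently: one with no reference at the decision point, the other against a value taken after three weeks of grape juice.

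**Working it through.** **Inputs.** Visit days from the assessment table: Visit 1 = 15, Visit 2 = 36, Visit 3 = 50, Visit 4 = 72. Lipid panels: Visits 2 and 4 (Section 8.0), total 2 (table). Allocation: half of the women to each sequence (Section 9.0), so about 10 of 20.

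**Lipid values available when the rule applies, as planned**

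| Sequence | Post-wine visit | Earlier lipid values | Study visits remaining |
|---|---|---|---|
| Wine-first | Visit 2 (day 36) | none | Visits 3 and 4 |
| Juice-first | Visit 4 (day 72) | one: Visit 2, post-juice | none |

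For wine-first women the next lipid value is at Visit 4, 72 − 36 = 36 days later. It follows the juice period, so a comparison is possible only in retrospect.

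**Could the table be read differently?** In the table as I could read it, the first lipid mark sits between the Visit 2 and Visit 3 marks of the other rows. Section 8.0 settles it as Visit 2. If it were Visit 3, juice-first women would have a washout reference, but wine-first women would still have nothing before Visit 2.

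**Could another source supply the reference?** Eligibility (Section 3.0) requires liver tests and sets limits on HbA1c or fasting glucose, each with a look-back window, but asks for no lipid result. No section provides for a medical-record triglyceride value. The stored Visit 1 sample is reserved for hormone assays at the end of the study, whereas Section 12.0 has safety results monitored in real time.

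**The other two triggers.** The liver limit is absolute and needs no earlier value. Blood counts are taken at all 4 visits, so a wine-first woman has a Visit 1 value at Visit 2. Only the triglyceride trigger lacks data.

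**With added panels**

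| Schedule | Wine-first: value before wine | Juice-first: latest washout value before wine |
|---|---|---|
| Add Visit 1 | Visit 1, 36 − 15 = 21 days earlier | Visit 1, 72 − 15 = 57 days earlier |
| Add Visits 1 and 3 | Visit 1, 21 days earlier | Visit 3, 72 − 50 = 22 days earlier |

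**The case against.** The strongest reply is that little protection is lost. The rule also requires an out-of-range value, and that part can be read at Visit 2 in both sequences. Any woman who could meet the rule is therefore visible to physicians who monitor results as they arrive, and the safety monitor follows up concerning results. The assigned wine is already finished, so discontinuing a wine-first woman at Visit 2 spares her only the rest of the study. All of this stands, and it limits the severity. It does not make the rule computable: discretionary review is a safeguard, but not the trigger that the protocol specified.

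Second, Section 12.0 does not ask for a washout reference, and panels at Visits 2 and 4 give every completer a wine and a juice value, which suits the period comparisons reported to the monitoring board. That is fair for group summaries. It does not help an individual decision at Visit 2.

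Third, the 15% blood-count rule names no comparator either. True, and worth tidying, but values exist for it in both sequences.

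Fourth, the manual of operations, which is not among the documents, may name a source. That cannot be excluded, but a reference that decides discontinuation should be in the protocol.

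**Conclusion.** The concern holds. Followed exactly, the plan leaves one of three laboratory triggers impossible to evaluate at the decision point for the wine-first half, about 10 of 20 women. For the other half it can be evaluated only against a post-juice value. It should be fixed, but it is a limited gap: backup review exists, the assigned wine is over when the rule applies, and the hormone analyses are unaffected.

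The figure of 10 assumes equal allocation among 20 completers. Section 23.0 enrols until 20 women complete, so the number randomized could be higher. The conclusion also assumes that no reference is defined outside the protocol.

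**What to change.** Add a lipid panel to the fasting draw already planned at Visit 1. This is the minimum change and gives every woman a washout value before wine. Adding one at Visit 3 as well gives juice-first women a reference immediately before their wine period. State in Section 12.0 that doubling is judged against the washout value directly before wine: Visit 1 for wine-first, Visit 3 for juice-first. Carry the change into Section 8.0, the Visit 1 and Visit 3 text, the assessment table and the tube list, which at present has no lipid tube even for the panels planned at Visits 2 and 4.

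**Cost, for 20 completers.**

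- Assays: 20 × 2 = 40 now; 20 × 3 = 60 with Visit 1; 20 × 4 = 80 with Visits 1 and 3. No extra visit.
- Blood, if each panel needs its own 10 mL tube: 100 + 3 × 90 = 370 mL listed now; 370 + 2 × 10 = 390 mL once the two planned panels are counted; 400 mL with Visit 1; 410 mL with Visits 1 and 3. If the laboratory can share a tube (an assumption), nothing is added. The statement on blood-volume guidelines should be rechecked.

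Replacing the doubling with an absolute triglyceride limit would need no new assay, but it changes the rule. The threshold and the action are for the clinical team. No option changes the fact that juice-first women reach the rule at their last visit, where only referral is meaningful; the same is true of the liver and blood-count triggers.
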